1. PROTOCOL RESUME

1.1. Protocol Resume

Protocol title:

Effect of White Tea (*Camellia sinensis* L.) Beverages on Anthropometric, Hematological, Biochemical and First Line Antioxidant Enzymes Activity of Healthy Human (Superoxide Dismutase, Catalase, and Glutathione Peroxidase)

Research aims:

Understanding the potential of white tea for human health in terms of anthropometry (body weight, body mass index and waist circumference), blood pressure and biochemistry (lipid profile, blood glucose levels and antioxidant enzyme activity). Furthermore, the safety of white tea products will be evaluated by means of haematological parameters (red blood cells, haematocrit, haemoglobin, mean corpuscular volume (MCV), and mean corpuscular haemoglobin (MCH)), liver parameters (alanine aminotransferase (ALT) and aspartate aminotransferase (AST)), and renal parameters (creatinine levels, estimated glomerular filtration rate (eGFR), and blood urea nitrogen) following a 14-day period of white tea consumption.

Study design:

This study will combine a pilot study with a pre-post quasi-experimental design.

Specific aims

1. Determine the effect of white tea consumption on the anthropometry of healthy subjects based on body weight, body mass index, waist circumference, and blood pressure.
2. Determine the effect of white tea consumption on the biochemical parameters of healthy subjects based on blood glucose, lipid profile (total cholesterol, low-density lipoprotein (LDL), high-density lipoprotein (HDL), and triglycerides), alanine aminotransferase (ALT), aspartate aminotransferase (AST), serum creatinine levels, estimated glomerular filtration rate (eGFR), and urea nitrogen levels.
3. Determine the effect of white tea consumption on blood parameters in healthy subjects based on red blood cell count, haemoglobin, haematocrit, mean corpuscular haemoglobin (MCH), and mean corpuscular volume (MCV).
4. Determine the effect of white tea consumption on the activity of first-line antioxidant enzymes (superoxide dismutase, catalase, and glutathione peroxidase) in healthy subjects.

Pre-post quasi-experimental study design

The present study was conducted over a period of 14 days with the aim of observing the effects of white tea consumption on anthropometric parameters, blood pressure, haematology, biochemistry, and antioxidant enzymes activity. Prior to the intervention, subjects were instructed to undergo a washout phase. During the washout phase, subjects were instructed to refrain from consuming vitamins, herbal drinks containing spices (turmeric, ginger, and galangal), fruits with high flavonoid content (grapes, apples, oranges, and their processed products), and products containing high levels of tannins (coffee, other types of tea, and chocolate). This approach was adopted to mitigate potential bias and to avert the occurrence of anemia or other forms of toxicity.

Subsequently, a series of anthropometric, blood pressure, complete haematology, and biochemistry tests are conducted to ascertain which subjects meet the criteria to proceed to the research stage. Subjects who meet the specified criteria will then be educated on the art of tea-making and instructed to consume it for a period of 14 days. During the administration stage of white tea, subjects are instructed to refrain from using the products that they abstained from during the washout stage. Anthropometric measurements, blood pressure, complete haematology, and biochemistry tests will be performed again on day 15 and the day after last day white tea administration. Subsequently, all subjects will undergo a period of post-intervention monitoring (the observation phase) for a duration of seven days. The purpose of this monitoring is to ensure that no deleterious effects result from the white tea intervention.

Sample Size Calculation

This study is a pilot study, and the minimum sample size calculation will be performed using the thumb method through an NCT approach with 90% power and a significance value of 5%. The calculation indicated that, given a 20% attrition rate, a sample size of 19 subjects was required for the study.

Subject:

The total number of subjects included in the study was 19, with an age range of 20-35 years (excluding women who were either unmarried or sexually inactive). These subjects resided in the vicinity of Padjadjaran University and had provided written consent by signing an informed consent form. The subjects must be in good health, have not been active smokers for a period of less than five years, and have no history of anaemia, cardiovascular disease, or liver and kidney disorders. The exclusion criteria employed are outlined below:

- a. Participants were required to take certain medications or vitamin supplements.
- b. The subjects reported experiencing discomfort during the administration of the product.
- c. Prior to the initiation of treatment, biochemical results were found to be outside the normal range.

Consent to Respondents

Informed consent will be requested by the research team before the washout period begins. Consent will be given in writing in the form of a signed consent form by the respondents.

Respondents Recruitment

The patient recruitment process was executed through the dissemination of advertisements utilising Google Forms, which were subsequently propagated via social media WhatsApp groups and Instagram. Following an initial screening process based on the information provided in the Google Forms by prospective research subjects, the research team made a selection based on inclusion criteria to obtain patients who met the specified criteria.

Test Product

The test product provided was 4 grams of white tea, packaged in a tea bag. The respondents were instructed to brew one tea bag in 200 mL of hot water for 10 minutes. The ingestion of the white tea should be scheduled for one hour prior to or two hours after breakfast.

Monitoring During Intervention

During the white tea intervention process, subjects will be monitored for food and beverage intake and daily activities. Please refer to Appendix 1 for a comprehensive overview of the daily data.

Research Duration

The research is estimated to take 28 days, including the first seven days for the washout phase, the second 14 days for the intervention phase, and the last seven days for the observational stage. This is to ensure that the subjects do not experience any serious effects as a result of the research.

Data Collection

All data pertaining to the study will be stored on CRFs/individual screening sheets. The data will be recorded in both soft and hard file formats on a daily basis.

Evaluation Criteria

Anthropometric measurements, blood pressure, haematology, and biochemistry tests will be conducted before the intervention and one day after the last intervention (day 0 and day 15). Anthropometric measurements, blood pressure, and blood sampling will be conducted at the Faculty of Pharmacy, Padjadjaran University. The biochemical examinations will be carried out at the clinical laboratory of the Bandung City Health Office, while the complete haematology and antioxidant enzyme examinations will be carried out at the Biomedical Laboratory of the Faculty of Medicine, Padjadjaran University. The results of the examinations conducted before and after the white tea intervention will be analyzed to ascertain the effect of white tea consumption over a period of 14 days. The types of food and beverages consumed by the research subjects and their daily activities were recorded in the CRF for a period of 28 days (from the wash-out phase to the observational phase).

Statistical Analysis

The effect of white tea administration will be compared before and after treatment using a t-test analysis.

1.2. Proposal Summary

Background

In the contemporary era, there is a general consensus that individuals have the capacity to procure a wide variety of goods and services with ease. A pertinent example of this phenomenon is the accessibility of food. A significant proportion of the population may be unconsciously adopting unhealthy lifestyles, characterised by the consumption of junk food in place of healthy foods, and an insufficient amount of exercise and rest, potentially attributable to their demanding workloads. These factors are supported by rapid industrial development, which also contributes to increased pollution, thereby increasing the production of free radicals in the human body. It is evident that the excessive and protracted generation of free radicals will exert a substantial influence on the onset of degenerative diseases, including cardiovascular disease, diabetes mellitus, cancer, and other grave pathologies.

The objective of the present study is to assess the antioxidant potential of white tea, with a view to providing the public with a reference point for high-antioxidant products that are more convenient and safer to consume. White tea has been shown to be effective in other countries, such as China, but the potential of white tea produced in Indonesia has not yet been extensively investigated. Geographical differences in the cultivation of tea have been demonstrated to result in discrepancies in content and effects. In the event of efficacy being demonstrated, it would be beneficial to conduct further testing of its potential in other, more specific diseases. Patients who meet the specified criteria will be instructed to consume white tea for a period of 14 consecutive days, while ensuring that they avoid the consumption of products that are rich in antioxidants, such as vitamins, herbal drinks (turmeric, ginger, and galangal), fruits with high flavonoid content (grapes, apples, oranges and their processed products), and products containing high tannin compounds (coffee, other types of tea, and chocolate). During the white tea consumption phase, subjects will be asked to report their daily food and beverage intake, as well as their daily activities. Clinical examinations will be conducted in two phases: the first prior to the administration of white tea, and the second after a 14-day period of white tea consumption. The data will be examined and compared before and after the administration of white tea to analyze the effects of white tea on human health. Should the study demonstrate a satisfactory degree of potential, it may be utilised as a point of reference to ascertain its broader potential for the treatment of specific diseases.

Metodologi

This study will analyze the potential effects of consuming white tea for 14 consecutive days. During the 7 days prior to white tea consumption (wash-out stage) and the 14 days during white tea consumption (treatment stage), all research subjects were instructed to avoid consuming products high in flavonoids, such as vitamins, herbal drinks containing spices (turmeric, ginger and kencur), fruits high in flavonoids (grapes, apples, oranges and their processed products), and products containing high levels of tannins (coffee, other types of tea, and chocolate). This was done to avoid excessive flavonoid intake, which can trigger anaemia and the formation of pro-oxidants. In addition, the presence of other strong antioxidants can also cause errors in the test (leading to bias) due to the influence of other antioxidant products. Furthermore, all respondents will be asked to drink white tea (made by brewing 4 grams of white tea in 200 mL of hot water) every morning one hour before eating or two hours after eating. To ensure the compliance of the research subjects, we will ask respondents to send videos of themselves consuming white tea, monitor and record the food and drinks consumed by all subjects in the CRF.

White tea is a type of tea that is believed to have better antioxidant content than other types of tea due to its high content of flavonoid compounds, especially catechins. If regular consumption of white tea for 14 days is proven to have a positive effect on anthropometric parameters, lipid profile, blood sugar levels and increases antioxidant enzyme activity, and is proven to be safe when reviewed from haematological parameters, ALT, AST, serum creatinine levels and eGFR, then this product can be further developed as a product for adjuvant therapy in various types of diseases. This study was conducted as an initial test of the potential of white tea for health before further exploration for application to a specific disease.

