The prevalence of degenerative diseases in contemporary society is attributable to a multitude of factors, chief among which is an unhealthy lifestyle that engenders excessive ROS formation. Antioxidants are vital for neutralizing and reducing ROS production in the body. White tea (*Camellia sinensis*) is one such antioxidant whose potential for exploration is significant (12). Catechins and polysaccharides have been identified as the bioactive compounds responsible for the wide range of biological activities exhibited by white tea, which include hypoglycemic, hypolipidemic, and antioxidant properties (13). Previous studies have reported that EGCG and EGC are capable of regulating gene expression in cholesterol metabolism, such as low-density lipoprotein receptor (LDLR), microsomal triglyceride transfer protein (MTTP), and apolipoprotein B (APOB) (14). Supported by other studies, white tea has been shown to suppress the adipogenesis process by increasing lipolytic activity (15). It has been documented that white tea has the capacity to reduce creatinine and blood urea nitrogen levels in female rats afflicted with kidney disorders induced by cisplatin (16). As demonstrated in our preceding preclinical research, a dose-response relationship has been observed between white tea consumption and several parameters, including ALT, AST, lipid profile, red blood cells, haematology, and haematocrit, in healthy rats. It was hypothesised that the most significant increase in ALT and AST values would occur at higher doses. This hypothesis was tested, and it was concluded that 0.072 mg/day of white tea (equivalent to a human dose of 4 g/day) was more effective than 0.144 mg/day (equivalent to a human dose of 8 g/day). This phenomenon may be attributable to the production of pro-oxidants, a consequence of the elevated antioxidant content present in high concentrations of white tea. The objective of this study was twofold: firstly, to analyze the effectiveness of a 4 g/day dose in humans on human health parameters; and secondly, to ensure the safety of using this dose for 14 days.

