8. STATISTICAL ANALYSIS

The mean data before and after treatment will be tested for homogeneity and normality. In order to draw parallels between the two data sets, parametric measurements will be considered using the T-test for data with normal distribution, while data with abnormal distribution will be analyzed using a non-parametric test, namely the Wilcoxon test. The statistical analysis of all data will be conducted using SPSS version 20.0.

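### Safety is a stated aim, but the day-15 safety values enter only a before-after difference test that cannot show safety in 15 to 19 people, and no per-subject or symptom summary is planned

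*Combined protocol and SAP*

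**What the plan says.** The research aims in Section 1.1 state that "the safety of white tea products will be evaluated by means of haematological parameters", liver enzymes "and renal parameters (creatinine levels, estimated glomerular filtration rate (eGFR), and blood urea nitrogen". That makes ten safety variables: RBC, haemoglobin, haematocrit, MCV, MCH, ALT, AST, creatinine, eGFR and urea nitrogen. Section 2.1 gives as its second objective "to ensure the safety of using this dose for 14 days". Section 1.2 makes safety, alongside benefit, a condition for taking the product forward: if it "is proven to be safe when reviewed from haematological parameters, ALT, AST, serum creatinine levels and eGFR, then this product can be further developed". The next sentence there tempers this: "This study was conducted as an initial test of the potential of white tea for health".

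On analysis, Section 1.1 says "The effect of white tea administration will be compared before and after treatment using a t-test analysis". Section 8 adds that "The mean data before and after treatment will be tested for homogeneity and normality", with a t-test for normal data, while "data with abnormal distribution will be analyzed using a non-parametric test, namely the Wilcoxon test". Neither place treats safety variables differently from efficacy variables.

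The data for a fuller account are collected. Section 7.5 has researchers record complaints, related to the tea or not. Appendix 1 has a seven-symptom checklist for each of 28 days, and a Final Screening form with a result and a status box for each laboratory parameter.

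**The concern.** A difference test asks whether the average moved. Safety in a small study turns on two other questions: how large a change the data still allow, and whether any individual moved out of range. A p-value above 0.05 answers neither.

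The stake is the development condition in Section 1.2. No planned analysis could meet it, so the report would have only p-values to offer against it. A sharp rise in one to three people could sit behind a non-significant group result. The symptoms, which are the most direct evidence on tolerability, have no place in the analysis section.

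**Working it through.** **1. Sample size.** Section 6 takes 15 from a rule-of-thumb table and allows 20% dropout: 15 / (1 - 0.20) = 18.75, rounded up to 19. The plan's figure reproduces. The 90% in that table is the power of a future main trial, not of any safety comparison here. The documents give no SD, margin or event rate for any safety variable.

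**2. A uniform shift.** Assume a paired t-test, two-sided at 5% (the documents state neither the pairing nor the sidedness). With d the mean change divided by the SD of change, the chance of missing it is the probability that a noncentral t with n-1 degrees of freedom and noncentrality d√n falls inside ± t(0.975, n-1).

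| d | missed, n=19 | missed, n=15 |
|---|---|---|
| 0.5 | 46% | 56% |
| 1.0 | 2% | 5% |

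A large common shift would be seen; a moderate one is close to a coin toss. The 95% interval half-width for the mean change, t(0.975, n-1)/√n, is 0.48 SD at n=19 and 0.55 SD at n=15.

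**3. A few individuals rise.** Assumed inputs, none in the documents: SD of ALT change 3, 5 or 10 U/L; no change on average in the other subjects; one to three subjects rising by 60 or 100 U/L. Section 8 names no normality test, so a Shapiro-Wilk test at 5% on the paired differences is assumed to choose between the t-test and the Wilcoxon signed-rank test. Share of simulated trials with p<0.05, n=15 and 19 together:

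| Affected subjects | t-test alone | Wilcoxon alone | Procedure with normality step |
|---|---|---|---|
| one, +60 or +100 | 0-2% | about 5% | about 4-6% |
| two, +60 | 0-6% | 8-9% | about 8-9% |
| three, +60 | 2-19% | 14-15% | about 13-16% |

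The normality step rejects in about 90-100% of these trials, so the last column is nearly the Wilcoxon test and is the one that describes the plan. For one affected subject it equals the false-positive rate. Only the ratio of rise to SD matters, so the CRF's use of µkat/L changes nothing. These rises are 6 SD (60/10) to 33 SD (100/3). For a smaller rise of 3-5 SD in one subject, the t-test is significant in 3-5% and Wilcoxon in 4-5%.

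**4. What counts would show.** With no out-of-range results, the upper end of the two-sided exact 95% interval is 1 - 0.025^(1/n): 17.6% for 0/19 and 21.8% for 0/15. Even a clean result leaves a substantial rate possible, and the report should say so.

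**5. Why counts are only descriptive.** Subjects are selected in range at day 0 and there is no control arm. If ranges cover 95% of people and the within-person correlation is 0.7-0.9 (assumed), 2.1-3.5% per variable fall out of range at day 15 with no tea effect. Counting any of ten independent variables gives 1 - (1 - 0.021)^10 = 19% to 1 - (1 - 0.035)^10 = 30% of subjects. Independence is doubtful, since Section 7.11 calculates eGFR from creatinine. Counts should therefore be reported per variable.

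**The case against.** The strongest reply is that the error is imputed. A reader might infer that the team will take p>0.05 as proof of safety. No sentence about this study says that: the wording in Section 1.2 is conditional, in a summary, and followed by a description of the study as an initial test. That stands. What remains is that no planned analysis could satisfy the condition.

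A reader might also infer that harm to an individual would go unnoticed. The documents do not support that. There is a seven-day observation phase (Section 4), results are signed as reviewed (10.1), the day-15 form has a status box per parameter, the audit verifies side effects (10.4), and subjects stopped for medical reasons are followed (7.6). A large rise should be seen by the team. But these are review steps. They commit to no tabulation, and the abnormality rules in Sections 6 and 7.5 cover only results before treatment.

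Third, the ALT inputs are assumed, and the t-test figures alone would overstate the problem because Section 8 checks normality first. That is right, so the conclusion uses the procedure with the normality step.

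Fourth, this is a 19-subject pilot. That argues for description with intervals rather than for relying on tests.

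**Conclusion.** The concern holds as a gap in planned analysis and reporting, worth fixing because it is cheap. A stated aim has only a difference test behind it, and at this size that test cannot show safety.

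The miss rates in step 2 and the exact limits in step 4 rest only on n, the 5% level and standard theory. The 4-16% rests on the assumed ALT inputs and the assumed normality test; its direction is firm, its exact value is not.

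It does not follow that the sponsor has committed to a false safety claim or that participants are unmonitored. Nor do the documents say that people removed under exclusion criterion b (discomfort during administration) will be left out of the report; they simply do not say who is counted. Section 5 was not in the text available for this review. The statements here rest on Section 1.1, Section 8 and the other sections cited.

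**What to change.** Keep the planned tests and add to Section 8:

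1. For each of the ten safety variables, a table of per-subject shifts from day 0 to day 15 against the laboratory ranges used for eligibility (stated once), with counts per variable and two-sided exact 95% intervals. List treated subjects without a day-15 sample, with the reason.
2. The mean change with its 95% interval.
3. Each checklist symptom and recorded complaint by phase (washout, intervention, observation), counting onsets after the first tea as on-treatment, with exact 95% intervals. The denominator is everyone who drank the tea, including anyone removed under exclusion criterion b.
4. A statement that p>0.05 is not evidence of safety, and that some out-of-range values are expected by chance because subjects are selected in range at day 0 and there is no control arm, so counts are descriptive. The protocol should not carry an expected number of chance flags, since that rests on assumed correlations.

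In Section 1.2, replace the requirement that safety be proven with: *shows acceptable preliminary tolerability, described by per-variable counts of out-of-range day-15 results and symptoms with 95% CIs*.

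The cost is a short paragraph, one or two table shells, the ranges and one reworded clause. No new measurements are needed. The downside is a weaker safety statement and a little more tabulation.

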1.3. List of Abbreviations and Definitions

ALT	: Alanine aminotransferase
APOB	: Apolipoprotein B
AST	: Aspartate aminotransferase
BMI	: Body mass index
CAT	: Catalase
CRF	: Case Report Form
EDTA	: Ethylene Diamine Tetra acetic Acid
EGCG	: Epigallocatechin Gallate
EGC	: Epigallocatechin
eGFR	: estimated Glomerular Filtration Rate
GPx	: Glutathione Peroxidase
Hb	: Hemoglobin
HCT	: Hematocrit
HDL	: High-density Lipoprotein
LDL	: Low-density Lipoprotein
LDLR	: Low-density Lipoprotein Receptor
MCV	: Mean Corpuscular Volume
MCH	: Mean Corpuscular Hemoglobin
MTTP	: Microsomal Triglyceride Transfer Protein
RBC	: Red Blood Cells
ROS	: Reactive Oxidative Stress
SOD	: Superoxide Dismutase

2. Introduction

